#### **7.4 WEB SYSTEMS**

The study will use two web systems: a computerized tracking system and REDCap. The computerized tracking system will contain all participant tracking details. This system will be web-based, allowing multiple users to access the system. REDCap is a secure web application for building and managing online surveys and databases and will be used for screening and assessment purposes. Study forms will be completed according to the schedule below.

FORM	Screen & Baseline Visit		Implant Visits	Medication Checks	6-month visit (24 weeks)	12-month visit (52 weeks)	As Needed
	Screen	Baseline					
Screener	X						
Consent and enrollment form	X						
Contact info		X	X	X	X	X	X
Phlebotomy form (Paper)			X		X	X	X
Full assessment		X			X	X	
Short assessment		X	X	X			
Contact log							X
Baseline Event Form		X					X
Medication use collection (Paper)		X	X	X	X	X	X
Baseline tracking form		X					
Follow-up tracking form		X	X	X	X	X	
Participant tracking overview							X
Participant tracking entry							
Study conclusion form							X
AE/SAE form (paper and Web)							X
Incarceration form							X
Naloxone challenge tracking form		X	X				
Medication form			X	X	X	X	X
Detox form							X
Qualitative interview tracking							X
Provider interview tracking							X
Case Manager forms							X

## 8. STATISTICAL ANALYSIS

This study will use an intent-to-treat analysis that includes all participants according to their randomized assignment. Descriptive statistics will be calculated for variables at baseline and each follow-up time to assess whether there appear to be any differences across treatment arms.

Our Specific Aims are to compare the effects of LINC-II and standard of care following outcomes:

a. Primary: Undetectable HIV viral load at 12 months

b. Secondary: Initiation of ART within 28 days of randomization;

Change in CD4 count from baseline to 12 months;

Retention in HIV care (i.e.,  $\geq 1$  visit to medical care in 2 consecutive 6 month periods)

Undetectable HIV viral load at 6 months;

HVL suppression and past 30-day opioid abstinence assessed at 6 and 12 months.

## 8.1 PRIMARY ANALYSES

The primary outcome for this aim is HIV viral load suppression at 12 months. Initial analyses will be performed comparing this binary outcome between groups using a chi-square test. The primary analysis will use multivariable logistic regression analyses to control for the stratification factor to improve efficiency, (i.e., ever ART use). If there are any baseline factors that appear to differ by randomized group, additional sensitivity analyses will be conducted controlling for these factors to assess for potential confounding. The secondary outcomes of undetectable viral load at 6 months, ART initiation within 28 days and retention in HIV care will be analyzed using the same approach described above. Change in CD4 count between baseline and 12 months will be analyzed using multiple linear regression adjusting for the stratification factor. If the distribution of change in CD4 is skewed, transformations of the data will be considered. If an appropriate transformation is not identified, a median regression model will be used.  

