### 2.3 STUDY OUTCOMES

[figure not shown]
**Aim 1.** The primary outcome for aim 1 is defined as an undetectable HVL at 12 months post randomization, assessed by study test within a window of 9–15 months. Secondary outcomes are initiation of ART within 28 days of randomization, change in CD4 count between baseline and 12 months (assessed by study test), retention in HIV care (at least 1 visit to medical care in 2 consecutive 6 month periods within 12 months of enrollment, assessed by medical record review and by self-report), undetectable HVL at 6 months post randomization assessed by study test, and a composite outcome for achieving both HVL suppression and past 30-day opioid abstinence assessed at 6 and 12 months.

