## 3.2 RANDOMIZATION

Randomization will be stratified based on one factor that could relate to study outcome: ever ART use. Blocked randomization using random block sizes will be used within each stratum. A computer-generated randomization table will be created to allow randomization to occur via a custom web-application.

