### 3.3.B. RAPID ACCESS TO ART

With all HIV-positive individuals now eligible for ART in Russia, regardless of CD4 count, participants randomized to the intervention, will have rapid access to antiretroviral medications. Rapid access to ART will be facilitated by the infectionist (HIV physician) employed by the City AIDS Center, who sees patients at the St. Petersburg CAH. All participants will meet with the infectionist and have their blood drawn for CD4 and HVL testing. The infectionist will order a blood draw for HVL and CD4 for all participants. The

blood will be sent to CAC for testing. All ART initiation requests in St. Petersburg must be approved by a special committee at the City AIDS Center. For participants randomized to the intervention group, the infectionist will streamline this approval with the ultimate goal of starting participants on ART while they are still hospitalized at CAH. If participant remains hospitalized at CAH at the time of ART approval, the infectionist will deliver the first set of medications (1-month supply) to the patient at CAH. Case Manager will help schedule the subsequent visit to the AIDS Center in 1 month to pick up the next refill of medication. If a participant is no longer admitted at CAH, CM will help patient schedule his or her visit to CAC as soon as possible, where the first set of medications will be provided. Once the initial visit to City AIDS Center is made, participants can continue HIV care at one of two possible sites: St. Petersburg AIDS Center or their local HIV outpatient clinic, and all subsequent ART refills can be picked up at a local clinic.

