1. CD4, HIV-1 RNA
  - a. Measured at baseline, 24- and 52-week study visits among control and intervention participants. Samples collected at City Addiction Hospital (baseline) and Pavlov University (follow-up) are sent to the City AIDS Center for testing. Results from the testing are placed in participant medical records at City AIDS Center and provided to the Pavlov University research team.

- i. If CD4 and HVL results are already available at the City AIDS Center within the 24- and 52-week visit windows, a new study test will not be conducted and existing results will be used.
  - ii. If recent (within one month) CD4 and HVL results are available at the City AIDS Center, a new baseline study test will not be conducted and existing results will be used.
  - iii. If a participant is unable to provide blood during their 6 or 12 month study visit and does not have a blood draw scheduled at the City AIDS Center within the study visit window, we will take the following approach:
    1. Control group: Participant will be invited to come in for a second blood draw attempt in 4 weeks. Participants will receive compensation in the amount of 500 rubles to cover costs associated with traveling to the laboratory.
    2. Intervention group: A second attempt at a blood draw will be made in 4 weeks (at their scheduled 28 week medication visit or after the completion of the 12 month visit). At the 28-week visit, participants will receive planned compensation for attending the medication visit but will not receive additional compensation for the blood draw. For the second attempt after the 12 month visit, participants will receive compensation in the amount of 500 rubles to cover costs associated with traveling to the laboratory.
  - iv. If a participant is unable to provide blood during their 6- or 12-month study visit due to COVID-19 restrictions and does not have a blood draw scheduled at the City AIDS Center within the study visit window, we will take the following approach:
    1. Control group: Participants will be invited back to Pavlov for a blood draw once restrictions are lifted. Participants will receive compensation in the amount of 500 rubles to cover costs associated with traveling to the laboratory.

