2. AST, ALT
  - a. AST/ALT will be measured only among intervention participants during implant visits 2, 3, and 4 to assess liver toxicity.
3. HIV Antibody Test
  - a. If a participant has an undetectable HIV viral load at baseline, an HIV antibody test will be conducted during their next study visit to verify their HIV status.

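### Baseline HVL, already collected in both arms, could be added to the primary viral-load model: an optional refinement worth about 0 to 3 points of power

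*Combined protocol and SAP*

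**What the plan says.** Section 2.3 sets the endpoint: "The primary outcome for aim 1 is defined as an undetectable HVL at 12 months post randomization". Section 8.1 plans a chi-square comparison, then a primary analysis by "multivariable logistic regression analyses to control for the stratification factor to improve efficiency, (i.e., ever ART use"). The 6-month viral-load outcome is handled the same way. The single covariate is the single stratifier in Section 3.2: "Randomization will be stratified based on one factor that could relate to study outcome: ever ART use".

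Other baseline variables enter only conditionally (Section 8.1): "If there are any baseline factors that appear to differ by randomized group, additional sensitivity analyses will be conducted controlling for these factors". The purpose given there is to look for confounding.

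Baseline HVL is available. Section 3.7.B, item 1, says of CD4 and HIV-1 RNA: "Measured at baseline, 24- and 52-week study visits among control and intervention participants". Section 3.3.B adds: "All participants will meet with the infectionist and have their blood drawn for CD4 and HVL testing". If the City AIDS Center holds a result from the past month, "a new baseline study test will not be conducted and existing results will be used". Entry with an undetectable value is foreseen in Section 3.7.B, item 3: "If a participant has an undetectable HIV viral load at baseline, an HIV antibody test will be conducted during their next study visit".

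No section puts baseline HVL in the model or gives a reason for leaving it out.

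**The concern.** When a model adjusts for efficiency, the baseline measurement of the outcome is usually the first candidate. Ever ART does not replace it. Ever ART records lifetime exposure, so someone treated years ago may enter with a high viral load, and it does not identify those who already meet the endpoint definition at entry. The imbalance-triggered analyses do not fill the gap either: they are secondary to the primary test and cannot add to its power.

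What is at stake is some power and some precision of the risk difference. Bias is not at stake.

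**Working it through.** **The plan's own figure.** Section 2.8.A gives alpha 0.05 (sidedness not stated; two-sided assumed), 192 evaluable participants, 10% vs 27%, and a continuity-corrected chi-square test. With 1:1 allocation (Section 2.4) that is 96 per arm, and d = 0.17.

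- Effective size after correction: (n − 1/d)²/n = (96 − 5.88)²/96 = 84.6 per arm.
- z = [d√n − 1.96√(2p̄(1−p̄))] / √(p0(1−p0) + p1(1−p1)), with p̄ = 0.185. At 84.6 per arm: (0.17 × 9.198 − 1.96 × 0.5491)/0.5358 = 0.909, so power is 81.8%. The stated 80% is met.
- Without the correction, at 96 per arm: (0.17 × 9.798 − 1.0763)/0.5358 = 1.100, so power is 86.4%. This is why the logistic tests below start at about 87%.

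**Where a gain could come from.** Section 2.8.A implies 0.10 × 96 = 9.6 control successes. Suppose 1 to 2% enter undetectable and 60 to 95% of them stay so (assumptions). They supply from 0.01 × 96 × 0.60 = 0.6 to 0.02 × 96 × 0.95 = 1.8 of the 9.6, or 6 to 19%. Adjustment removes the noise from their chance split between arms.

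**Size of the gain.** All simulations use 96 per arm with overall rates held at 10% and 27%, and compare arm + ever ART with arm + ever ART + baseline HVL at two-sided 5%. Every input on baseline HVL is an assumption.

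| Assumed form of baseline HVL | Cases | Power gain (points) |
|---|---|---|
| Continuous log HVL, odds ratio per SD | 1.0 / 1.25 / 1.5 / 2.0 / 2.5 / 3.0 | −0.3 / +0.4 / +0.8 / +2.1 / +3.0 / +4.4 |
| Undetectable yes/no, common odds ratio 4 | share 1% / 2% / 5% | −0.2 / +0.4 / +0.5 |
| Same, odds ratio 8 | 1% / 2% / 5% | +0.5 / +0.6 / +3.0 |
| Undetectable, 60% stay so in both arms | 1% / 2% / 5% | +0.7 / +0.8 / +2.6 |
| Same, 80% | 1% / 2% / 5% | +0.6 / +1.6 / +4.9 |
| Same, 95% | 1% / 2% / 5% | +1.3 / +2.9 / +7.6 |
| 50% stay so in control, 80% in intervention | 1% / 2% / 5% | +0.1 / +1.0 / +2.4 |
| Undetectable status not prognostic | 1% / 2% / 5% | −0.2 / −0.3 / −0.2 |

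The continuous rows use Wald tests with 6,000 runs; Monte Carlo error is about 0.5 point on each power. The binary rows use Firth likelihood-ratio tests: 2,500 paired runs for the common odds ratios (SE of gain 0.3 to 0.4) and 10,000 for the rest (SE 0.1 to 0.3). With 30% persistence the gain was +0.3 at a 2% share and 0.0 at 5%. Repeating the fixed-persistence model with separate code gave +0.5 to +0.8 at 1% (60 to 80% persistence), +0.1 to +2.3 at 2% and about +2.1 at 5%.

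The cells above 3 points are not relied on. A 5% share with 80% persistence needs 0.05 × 96 × 0.80 = 3.8 of the 9.6 control successes (40%) to come from people undetectable at entry. With 95% persistence it is 4.6 (48%). The continuous case above 3 needs an odds ratio of 3 per SD.

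**How the gain shows.** In a logistic model it does not appear as a smaller standard error. At a 2% share and 80% persistence, the mean log odds ratio (SE) moves from 1.21 (0.417) to 1.29 (0.438), while the variance of the standardised risk difference falls by 3.9%.

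**Type I error.** With both arms at 10%, it was 4.7 to 4.8% without and 4.3 to 4.6% with the binary covariate (Firth), and 4.4% and 4.7% with the continuous one (Wald). There is no material inflation.

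**The case against.** Nothing in the plan is wrong. Adjusting for the stratifier matches the design, and the reference to efficiency explains that adjustment without promising the most efficient model. The planned logistic test already has about 87% power under the plan's own rates.

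The documents also point to the low end. Section 2.7 excludes ART use in the 30 days before hospitalisation, and Section 3.7.B has HIV status re-verified when baseline HVL is undetectable. At a 1% share, 0.99^192 = 14.5% of trials would have no undetectable entrant at all. The equal-persistence rows are strong assumptions: they give undetectable entrants no treatment effect. At 60 to 80% persistence they imply odds ratios for baseline status of about 14 to 59 in controls and 4 to 13 in the intervention arm. With a common odds ratio of 4 or 8, gains at 1 to 2% shares are hardly distinguishable from zero.

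Baseline HVL is also less clean than ever ART, which must be known in order to randomise. The HVL result may be a month old, and Section 4.4 lists the blood draw after randomisation.

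All of this stands as regards size and priority. It does not supply a reason for omitting the variable, and the timing problem can be handled by definition.

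**Conclusion.** The point holds as an optional refinement. Adding baseline HVL would gain about 0 to 3 points of power. This rests on the rates and evaluable numbers in Section 2.8.A and on assumed values for the distribution and prognostic strength of baseline HVL.

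Three stronger readings are not supported:

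- A reader might infer that the primary analysis is biased or underpowered without this covariate. Randomisation protects the comparison, and the stated power is reproduced.
- A reader might infer a dependable gain of at least 1 point. Several reasonable cells lie below that. If 12-month suppression depends mainly on ART uptake after entry, the gain could be nil.
- A reader might take the order of items in Section 4.4 to mean that baseline HVL is a post-treatment value. Section 3.6 places it at the baseline visit, and the list is not stated to be a strict sequence. The ambiguity calls for a definition and does not rule the covariate out.

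Continuous and binary forms were simulated separately. The combined form proposed below, and missing baseline values, were not simulated.

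**What to change.** In Section 8.1, before outcomes are seen by arm, prespecify baseline HVL next to ever ART in the 6- and 12-month viral-load models:

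- **Form:** log10 HVL, with values below the detection limit set to a stated fixed value, plus an undetectable indicator. State a minimum pooled count below which the indicator is dropped.
- **Timing:** the last value sampled before any study ART is started.
- **Missing values:** keep participants with no qualifying value through a missing-indicator category, so that the covariate removes nobody from the intention-to-treat set in Section 8.
- **Separation:** use Firth logistic regression if it occurs.
- **Reporting:** give a standardised risk difference beside the odds ratio.

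No new visit, test or procedure is needed. The costs are a little more analysis-plan text and code, an odds ratio that becomes conditional on baseline HVL, and a possible nil gain or a loss of about 0.3 points if baseline HVL is not prognostic.

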#### 2.8.A. SAMPLE SIZE CALCULATION AND POWER

We provide power calculations for the key hypotheses to be tested in this RCT. Sample size calculations assume an alpha level of 0.05 and 240 patients enrolled into the trial.

**Aim 1: primary study outcome, undetectable viral load at 12-months post randomization:** Based on data from the LINC study, we expect 10% of controls will have undetectable viral load at 12 months. Given this and assuming 20% loss to follow-up (i.e., 192 evaluable subjects) the study will have 80% power to detect an absolute difference of 17% (i.e., 27% vs. 10% in the intervention and control arms, respectively) using a chi-square test with continuity correction. We anticipate larger effects may be observed in our study, which would result in even higher power.

**Aim 1: secondary study outcome, retention in HIV care (within 12 months):** Because this secondary outcome will be assessed using medical records, we expect loss to follow-up to be minimal and estimate 10% loss to follow-up due to death and subject withdrawals. Based on data collected from LINC, we expect 20% of controls will attend 2 appointments in 12 months. Based on these assumptions and with 216 evaluable subjects, the proposed study has 80% power to detect an absolute difference of 19% (i.e., 39% vs. 20% in the intervention and control groups, respectively) in the proportions retained in HIV care, based on a chi-square test with continuity correction.

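### The model for 12-month CD4 change omits baseline CD4, which every analysed participant already has, so this secondary analysis generally gives up precision

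*Combined protocol and SAP*

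**What the plan says.** Section 8.1 gives the CD4 outcome one modelling sentence: "Change in CD4 count between baseline and 12 months will be analyzed using multiple linear regression adjusting for the stratification factor". Section 3.2 identifies the factor: "Randomization will be stratified based on one factor that could relate to study outcome: ever ART use". The specified covariate set is therefore ever ART use alone.

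If the change is skewed, Section 8.1 first considers transformations and then says "If an appropriate transformation is not identified, a median regression model will be used". Neither fallback mentions baseline CD4.

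Baseline CD4 is available. Section 3.7.B says of CD4 and viral load: "Measured at baseline, 24- and 52-week study visits among control and intervention participants". The schedules in Section 3.6 show the same for each arm.

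Two other statements in Section 8.1 bear on the point. The primary logistic model is adjusted "to control for the stratification factor to improve efficiency". A further adjustment depends on the data: "If there are any baseline factors that appear to differ by randomized group, additional sensitivity analyses will be conducted controlling for these factors".

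**The concern.** The plan gives efficiency as its reason for covariate adjustment. In the CD4 analysis the same reason applies to the baseline value of the measurement being analysed, yet that value is left out.

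A change score without a baseline term fixes the slope of 12-month CD4 on baseline CD4 at 1. If the slope differs from 1, two things follow, and they are one loss seen from two sides. The standard error is larger than it need be, and part of any chance baseline difference between arms stays in the estimate.

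The imbalance-triggered sensitivity analysis does not fill the gap. Its sentence follows the binary primary model. The outcomes said to share that approach are 6-month viral load, ART initiation and retention, while CD4 gets its own sentence. Even read as covering CD4, it has no stated criterion, is aimed at confounding and leaves the main estimate as it was.

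At stake is the precision of one named secondary comparison. Neither its validity nor the primary result is in question.

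**Working it through.** **No plan figure to reproduce.** Section 2.8.A powers viral load and retention only. The documents give no SD, correlation, effect size or power target for CD4.

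**Inputs from the documents.** 120 randomised per arm (Section 2.4) and 192 evaluable at 12 months, so 96 per arm (Section 2.8.A). The 192 is stated for viral load and is borrowed here for CD4.

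**Assumed inputs.** *r* is the correlation of baseline and 12-month CD4, and *k* = s1/s0 is the ratio of the 12-month SD to the baseline SD. Both are taken within levels of ever ART use, since both models contain that term.

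**Variance of the treatment estimate**, in units of 2/96:

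- Planned model: s0² + s1² − 2·r·s0·s1
- With baseline CD4 added: s1²(1 − r²)
- Difference: (s0 − r·s1)², which is never negative and is zero only when r·k = 1, that is, at slope 1

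The ratio, adjusted over planned, is V = k²(1 − r²) / (1 + k² − 2rk). With k = 1 it reduces to (1 + r)/2. Worked example at k = 1.25 and r = 0.5: 1.5625 × 0.75 / (1 + 1.5625 − 1.25) = 1.1719/1.3125 = 0.893.

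| r | k = 0.8 | k = 1 | k = 1.25 | k = 1.5 |
|---|---|---|---|---|
| 0.5 | 0.57 | 0.75 | 0.89 | 0.96 |
| 0.7 | 0.63 | 0.85 | 0.98 | 1.00 |
| 0.8 | 0.64 | 0.90 | 1.00 | 0.95 |
| 0.9 | 0.61 | 0.95 | 0.95 | 0.78 |

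**As sample size (192/V), for r = 0.5, 0.7, 0.8, 0.9.** With k = 1, the adjusted analysis of 192 is worth about 256, 226, 213 and 202 participants under the planned model. With k = 1.25 it is worth about 215, 196, 192 and 202.

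**As power, k = 1, two-sided 0.05.** A difference that the planned model detects with 80% power would be detected with about 90%, 86%, 84% and 82%.

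**Simulation check.** Trials of 96 per arm, with a binary stratum in both models:

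- 3,000 trials, k = 1: variance ratios 0.75, 0.85 and 0.97 at r = 0.5, 0.7 and 0.9.
- 4,000 trials, k = 1: 0.75, 0.87, 0.91 and 0.95 at r = 0.5, 0.7, 0.8 and 0.9.
- 4,000 trials, k = 1.25: 0.90 at r = 0.5 and 1.00 at r = 0.8, the no-gain case.

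Mean error was about zero for both models.

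**The same loss seen as chance imbalance, k = 1.** The difference in baseline means has standard error √(2/96) = 0.144 SD, so its 95% range is ±1.96 × 0.144 = ±0.28 SD. With slope r, an imbalance at that edge moves the planned estimate by (1 − r) × 0.283 = 0.141, 0.085 or 0.028 SD at r = 0.5, 0.7 or 0.9. The planned estimate's standard error is √(2(1 − r)) × 0.144 = 0.144, 0.112 or 0.065 SD. The shift is therefore 0.98, 0.76 or 0.44 of a standard error. An imbalance of one standard error shifts it about half as much.

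**The case against.** The strongest reply is that nothing here is an error. A change-score model adjusted for the stratification factor is coherent, prespecified and unbiased, and CD4 has no power target to miss. That is correct, and it limits the point to an efficiency recommendation.

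Second, the gain may be close to nil. Section 2.7 excludes ART use in the 30 days before admission, and the planning rates for viral suppression at 12 months are only 27% and 10%. Mixed treatment response could widen the 12-month spread. At k = 1.25 and r from 0.7 to 0.9, the standard error falls by at most about 2.5%. This stands as a caution about size. It does not settle the matter, because mixed response may also lower r.

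Third, chance imbalance should not be counted as a second harm. This also stands. At r = 0.5 and k = 1 the planned variance of 1.00 is the adjusted 0.75 plus (1 − 0.5)² = 0.25, so the planned standard error already contains it and interval coverage is not affected.

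Fourth, the least-squares formula does not cover the median-regression fallback. A small simulation with a skewed baseline (600 trials, some convergence warnings) gave variance ratios of about 0.82 to 0.92 at r = 0.5 to 0.7 with equal SDs. It gave 1.00 to 1.04 at r = 0.9, or at k = 1.25 with r = 0.8. A gain there is plausible but not assured; the reason for including baseline CD4 in that model is mainly consistency.

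None of this gives a reason to leave baseline CD4 out of the linear model.

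**Conclusion.** The point holds as a recommended improvement to one secondary analysis. The CD4 model omits a baseline value that everyone with a change score has. In large samples the planned model is never more precise than the same model with baseline CD4 added, and it is equally precise only at slope 1.

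The omission is certain from the text; its size is not. With equal SDs and r between 0.5 and 0.9, the adjusted variance is 5% to 25% lower. With k = 1.25 it is 0% to 11% lower. These ranges rest on assumed SD ratios and correlations and, for the sample-size equivalents, on carrying the 192 evaluable over from viral load.

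**What to change.** Replace the CD4 modelling sentence in Section 8.1 with wording such as: *The 12-month CD4 change will be modelled by linear regression on randomised arm, with baseline CD4 and ever ART use as covariates.*

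Extend the fallback to match: *If the change is transformed, or if median regression is used instead, the model will keep the same two covariates.* Add a clause stating the scale on which baseline CD4 enters when the change is transformed. Define baseline CD4 as the value used to form the change score.

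The cost is SAP wording and one degree of freedom. No new data are needed and nobody is excluded, because a change score cannot exist without the baseline value. In the no-gain case the simulated variance ratio for the linear model was 1.00, so the downside is negligible. Fixing the covariate in advance also removes a later choice between adjusted and unadjusted results if baseline CD4 turns out to differ between arms.

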### Mediation

Exploratory analyses will be conducted to assess potential mechanisms that may drive LINC-II's ability to improve HIV care outcomes using the Baron and Kenny approach. The 3 potential mediators we will explore are decreases in substance use, HIV stigma, and substance use stigma. However, because the interpretation of the degree of mediation in logistic models is complicated by their inherent nonlinearity, we will conduct additional analyses using the recently developed causal inference approach to mediation (also referred to as the counterfactual framework), an approach that allows potential interactions between the interventions and mediators and derives direct and indirect effects for binary outcomes. We will use the Stata mediation package to conduct these analyses.

### Aim 2

The analyses for this aim will be descriptive in nature; formal hypothesis testing will not be conducted. Descriptive statistics (e.g., means, medians, interquartile ranges, and confidence intervals) will be obtained to assess quantitative data from provider, administrator, and patient surveys over time on perceptions and experiences of coordinated care. We will also conduct repeated measures analyses of

patients' attitudes and experiences using mixed effects regression models controlling for randomized group to assess overall changes over time and to explore and describe potential differences between study arms. Qualitative interview data will be analyzed following a thematic approach. Content analysis of qualitative data will reveal themes regarding care coordination and will identify best practices for LINC-II implementation in similar settings, (e.g., where addiction and HIV care systems are largely separate). Qualitative and quantitative results will be triangulated.

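### The 24-week CD4 enters no between-arm model or missing-data method, so the planned 12-month CD4 regression by default omits participants without a 12-month value

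*Combined protocol and SAP*

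**What the plan says.** All references are to the combined protocol and SAP.

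- **Measurement.** Section 3.7.B, item 1, on CD4 and HIV-1 RNA: "Measured at baseline, 24- and 52-week study visits among control and intervention participants". The schedule in Section 3.6 agrees for both arms.
- **Outcome.** The only CD4 outcome in Section 8 is the secondary one, "Change in CD4 count from baseline to 12 months".
- **Model.** Section 8.1: "Change in CD4 count between baseline and 12 months will be analyzed using multiple linear regression adjusting for the stratification factor". For skewed data a transformation is considered first, and then: "If an appropriate transformation is not identified, a median regression model will be used". Both fallbacks still concern the 12-month change alone.
- **Analysis set.** Section 8: "This study will use an intent-to-treat analysis that includes all participants according to their randomized assignment". No rule for missing CD4 follows.
- **Other use of the 6-month value.** Section 8: "Descriptive statistics will be calculated for variables at baseline and each follow-up time". This covers 6-month CD4 as a summary by arm.
- **Repeated-measures models.** Section 8.2 plans them under Aim 2 only, for "patients' attitudes and experiences using mixed effects regression models controlling for randomized group to assess overall changes over time".
- **Expected loss.** Section 2.8.A sizes the primary outcome "assuming 20% loss to follow-up (i.e., 192 evaluable subjects"). No loss, SD, effect size or power is given for CD4.

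**The concern.** A change score does not exist without its 12-month end. With no imputation rule, the Section 8.1 regression runs on participants with both values, and a week-24 CD4 obtained from someone later lost contributes nothing to the arm comparison. This is valid only if, within arm and ART-history stratum, loss is unrelated to the CD4 change.

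There are reasons in the design to doubt that, and to expect loss to differ by arm. Intervention participants are invited every 4 weeks and have a case manager for 12 months, while controls have two follow-up visits (Sections 2.4, 3.1 and 4.4). An existing City AIDS Center result inside the visit window replaces a study draw (Section 3.7.B), so someone engaged in HIV care can have a CD4 value without a study draw and someone out of care cannot. Phone assessments (Sections 4.6 and 5.2) yield no blood. If controls whose CD4 is falling are lost more often, the remaining controls look too healthy and the CD4 effect is understated.

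**Working it through.** **1. The plan's own figure.** There is none for CD4. The nearest is the primary-outcome power in Section 2.8.A: 240 × 0.80 = 192, or n = 96 per arm, with 27% vs 10%. Two-sided 0.05 is assumed, because sidedness is not stated. With continuity correction, power = Φ[(0.17 − 1/96 − 1.96·√(2·0.185·0.815/96)) / √((0.10·0.90 + 0.27·0.73)/96)] = Φ(0.0497/0.0547) = 81.8%, against 80% stated. It reproduces.

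**2. Number affected.** If the same 20% applies to CD4 (an assumption), 240 − 192 = 48 have no 12-month CD4, or 24 per arm. Let f be the share of these with a 6-month value. It is not documented. For f = 0.25 to 1, that is 12 to 48 people.

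**3. Precision.** Let r be the correlation between the 6- and 12-month changes (assumed 0.5 to 0.8). If loss is unrelated to CD4, the variance of an arm's mean 12-month change, relative to completers only, is (1 − r²) + r²·96/(96 + 24f). The detectable difference at 80% power is (1.960 + 0.842)·√(2/n).
- Planned: n = 96, giving 0.404 SD.
- r = 0.5, f = 0.25: ratio 0.75 + 0.25·96/102 = 0.985; effective n 97.4; 0.401 SD.
- r = 0.8, f = 1: ratio 0.36 + 0.64·96/120 = 0.872; effective n 110.1; 0.378 SD.
- Power for 0.404 SD rises from 80% to between 80.6% and 85.1%.

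**4. Bias, simple bound.** Suppose that in one arm only, those lost had a 6-month change worse by g SD. The completers-only bias in that arm's mean is [24f/(96 + 24f)]·r·g. With g = 0.5: (6/102)·0.5·0.5 = 0.015 SD for f = 0.25, r = 0.5; and (24/120)·0.7·0.5 = 0.070 SD for f = 1, r = 0.7.

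**5. Bias, simulation.** Assumptions, none from the documents except 120 per arm: SD 200 cells; correlations 0.75 (baseline–6 months), 0.80 (6–12) and 0.70 (baseline–12); true 12-month effect 40 cells; about 17–20% missing at 12 months; f = 0.75 unless stated; 3,000 trials per setting. The slope is the log-odds of loss per cell of 6-month CD4 fall. Rows marked * set a 6-month effect of 30 cells. A dash means not tabulated.

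| Loss at 12 months | Planned change score | Completers, baseline-adjusted | Using 6-month CD4 |
|---|---|---|---|
| Unrelated to CD4 | unbiased | unbiased | unbiased |
| Slope 0.003 in both arms* | 40.2 | – | – |
| Slope 0.005 in both arms* | 38.7 | – | – |
| Slope 0.001, controls only* | 36.3 | – | – |
| 0.003 in controls, 0.0015 in intervention* | 35.6 | – | – |
| Slope 0.003, controls only | 32.5 | 34.1 | 38.8 |
| Slope 0.005, controls only | 27.4 | 30.1 | 38.2 |
| Slope 0.005, controls only, f = 0.25 | 26.5 | – | 32.3 |

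For the planned analysis with f = 0.75, (32.5 − 40)/40 = −19% and (27.4 − 40)/40 = −32%. A separate set of runs of the same two settings gave 31.3 and 26.8, or −22% and −33%. With the 6-month value the bias is −3% and −5%.

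With unrelated loss the standard error is 21.7 for the planned analysis, 20.2 after baseline adjustment and 19.6 with the 6-month value added. So 1.5 of the 2.1 cells gained come from baseline adjustment. The bias is (40 − 32.5)/21.7 = 0.35 to (40 − 27.4)/21.7 = 0.58 standard errors.

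**The case against.** Regression on a change score is a conventional pre-specification, and CD4 is one of several secondary outcomes. The plan limits missing 12-month values through a window of 271 to 455 days (Section 3.6.A), use of City AIDS Center results in that window, repeat draws and chart entry (Section 3.7.B). The bias also depends on the scenario: with the same dependence on CD4 in both arms it all but vanishes, and nothing in the documents shows that dependence would be confined to controls. All of this stands and limits the weight of the point. None of it supplies a method for the values that remain missing.

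A reader might infer more than the text supports:
- *That no analysis uses the 6-month CD4.* Section 8 plans descriptive statistics at each follow-up. Only the between-arm model and missing-data handling lack it.
- *That the plan drops participants without a 12-month CD4.* It never says so. Omission is the default behaviour of the stated model, in tension with the intent-to-treat sentence.
- *That a 6-month value is in hand for everyone.* The draw is scheduled for everyone, but draws can fail and phone visits give no blood.
- *That 20% will lack a 12-month CD4.* That figure is stated for viral load.
- *That a bias of a fifth to a third is to be expected.* It is the one-arm worst case under assumed inputs.

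**Conclusion.** The point holds as a cheap improvement to a secondary analysis. A scheduled measurement that could inform missing 12-month CD4 values is left out of the arm comparison, and the plan gives no other handling.

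Under the assumed inputs the bias lies between near zero and about −20% to −33%, at worst roughly half a standard error. The upper end needs CD4-related loss in controls only. How much the 6-month value recovers depends on how many of those missing have one: most of the bias at f = 0.75, but only from 26.5 to 32.3 of 40 cells at f = 0.25. The precision gain is small, at most about 5 power points over the range examined. The case for change rests on validity when loss depends on the 6-month CD4, not on power. The primary outcome and its sample size are untouched.

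**What to change.** In Section 8.1, replace the single-timepoint CD4 regression with a longitudinal linear model:
- outcomes: baseline, 6- and 12-month CD4;
- terms: visit, arm-by-visit with a common baseline mean, and ever ART use;
- unstructured covariance;
- all randomised participants with any CD4 included.

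Report the 12-month arm contrast as the endpoint. Because the baseline mean is common, this is also the contrast in change from baseline, so the outcome is unchanged. Baseline adjustment, the source of most of the precision gain, is built in.

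Carry the skewness steps over explicitly: apply any transformation to the CD4 values in this model, and keep the planned median regression of 12-month change as a sensitivity analysis if skewness persists. State how CD4 after death is treated. Settle the wording before outcome data are seen by arm.

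The cost is revised text and a slightly more complex model, of a kind already planned under Aim 2, with no new data. The model relies on missingness at random given earlier CD4. That is an untestable assumption, but a weaker one than the completers-only analysis makes implicitly.
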